The escalation of care for patients in a hospitalized setting between nurse practitioner managed services, teaching services, step-down units, and intensive care units is critical for appropriate care for any patient. Often such "triggers" for escalation are initiated based on the nursing evaluation of the patient, followed by physician history and physical exam, then augmented based on laboratory values. These "triggers" can enhance the care of patients without increasing the workload of responder teams. One of the goals in hospital medicine is the earlier identification of patients that require an escalation of care. We have developed a model through a retrospective analysis of the historical data from the Mount Sinai Data Warehouse (MSDW), which can provide machine learning based triggers for escalation of care (Approved by: IRB-18-00581). This model is called "Medical Early Warning Score ++" (MEWS ++). This IRB seeks to prospectively validate the developed model through a pragmatic clinical trial of using these alerts to trigger an evaluation for appropriateness of escalation of care on two general inpatients wards, one medical and one surgical. These alerts will not change the standard of care. They will simply suggest to the care team that the patient should be further evaluated without specifying a subsequent specific course of action. In other words, these alerts in themselves does not designate any change to the care provider's clinical standard of care. We estimate (see "Narrative" section for details) that this study would require the evaluation of ~ 18380 bed movements and approximately 30 months to complete, based on the rate of escalation of care and rate of bed movements in the selected units (9W, 9E, 10W, 10E).

IF Number

IF2411760

2. Summary - Setup

Funding Has Been Requested / Obtained	No
Application Type	Request to Rely on Mount Sinai IRB
Research Involves	Prospective Study ONLY
Consenting Participants	No
Humanitarian Use Device (HUD) Used Exclusively in the Course of Medical Practice	No
Use of an Investigational Device to Evaluate Its Safety or Effectiveness	No
Banking Specimens for Future Research	No
Cancer Related Research that Requires Approval from the Protocol Review and Monitoring Committee (PRMC).	No

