6. Subjects - Enrollment

Site Name The Mount Sinai Hospital
Subjects To Be Enrolled
18680
Total Number of Subjects to be Enrolled Across All Listed Sites Above (Auto Populated) 18680

7. Subjects - Setting and Resources

Setting of Human Research Other

Specify Other Setting of Human Research

Hospital Units on 10W, 10E, 9W, 9E.

Total Number of Subjects Needed 18680

To Complete Study

Feasibility of Meeting Recruitment Goals

Our initial observation shows the rate of escalation ~ 10% for the selected units (10W and 10E). The estimated sample size is ~ 934 escalations of care which we expect to observe by including ~9340 bed movements. The estimated bed movements per day in the selected units is ~ 10 which makes the expected pilot days ~ 934 days (~ 2.5 yrs.). We anticipate an equal number of escalations for 9W and 9E, which will not receive any MEWS++ alerts.#

Facilities To Be Used for Conducting Research

Hospital Units on 9W, 9E, 10W, 10E

Multi-Center Study No

Community-Based Participant Research Study No

PI must attest to the following.

**** Process is adequately described to ensure that all persons assisting with the trial are adequately informed about the protocol, the investigational product(s), and their trial-related duties and functions.***

8. Subjects - Populations

Inclusion Criteria

All patients age 18 or greater who were admitted to a general care unit on 9W, 9E, 10W, 10E.

Exclusion Criteria

Any admitted patient who has a "Do Not Resuscitate (DNR)" and/or a "Do Not Intubate (DNI)" order in the EHR, any patient made "level of care" by RRT as documented in REDCap.

Enrollment Restrictions Based No

**Upon Gender, Pregnancy,
Childbearing Potential, or Race**

Age Range(s) 18 to 64 Years, 65 Years and Over

Targeted Population(s) Adults - Patients

Other Aspects that Could Increase Subjects Vulnerability

Prisoners and non-laboring pregnant women will be included if they are admitted to 10E/W or 9E/W. This will be rare but possible. Incapacitated patients will be provided the study information sheet within their paper chart and included unless their health care proxy/legally authorized representative chooses to opt them out of the study. If they were to regain consciousness and capacity, then they would have the ability to withdraw from the study."

Safeguards to protect Subjects rights and welfare

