Receipt or Transmission of Data	No
Holding Code That Can Be Linked to Identity of Participants	No

Duration Data Will Be Stored

Data are stored in accordance with the data retention policy of the manuscript in which the results will be published. This may vary by publication but is generally 7 years.

Steps That Will Be Taken to Secure the Data During Storage, Use, and Transmission

Only the designated investigator and co-investigators as listed on this form will have access to patient data used in this study and will be the sole arbiters for receipt and transmission of this data. The data will be password protected on Mount Sinai computers. Data are encrypted both at rest (i.e., when stored in the database) and while in motion (i.e., during transit between various components of the alerting system) using industry standard encryption protocols. Data will only be accessed from within the Mount Sinai network to ensure confidentiality, which is also password protected and physical access restricted. Any presentation will separate the presented material from the associated identifiers. All individuals have completed institutionally approved HIPAA training.

Power Analysis/Data Analysis Plan (Including Any Statistical Procedures)

Sample size calculation

Based on the pilot feasibility study, the current true rate of escalation of care in the selected units is ~ 10%. We expect that MEWS++ will identify at least 50% of the escalations, on average ~ 6 hrs before the expected time of deterioration/escalation. It is estimated that RRT and front-line providers collaboratively will be able to prevent ~ 20% of the predicted escalations. We are specifying a non-inferiority or superiority margin of 5%. As a result, the estimated sample size needing to achieve a type 1 error of 5% and power of 95% is 934. based on the rate of escalation ~ 10%, a total of approximately 9340-bed movements will need to be recruited for this study in the MEWS++ group and a total of 18680-bed movements across both groups. We assumed that there is not a significant

difference in the escalation rate between the selected units (10E and 10W) and control units (9E and 9W). Interim evaluations every 6 month will be conducted and if at any point the model meets statistical significance or major flaws identified, a subsequent report will be submitted.

Statistical Analysis:

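### The stated 95% power does not describe the two-arm design of 9,340 bed movements per arm, and the documents do not show how 934 was obtained or what it counts

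*Combined protocol and SAP*

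**What the plan says.** Section 19 (Sample size calculation) starts from an escalation rate of about 10%. It adds two assumptions about effect: "We expect that MEWS++ will identify at least 50% of the escalations" and "It is estimated that RRT and front-line providers collaboratively will be able to prevent ~ 20% of the predicted escalations". It then gives a 5% margin, described as non-inferiority or superiority, and concludes that "the estimated sample size needing to achieve a type 1 error of 5% and power of 95% is 934". Neither the formula nor the sidedness is stated. From 934 and the 10% rate it concludes that "a total of approximately 9340-bed movements will need to be recruited for this study in the MEWS++ group and a total of 18680-bed movements".

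Section 7 (Feasibility of Meeting Recruitment Goals) gives the same number a unit: "The estimated sample size is ~ 934 escalations of care which we expect to observe by including ~9340 bed movements". It sets the accrual rate: "The estimated bed movements per day in the selected units is ~ 10", hence 934 days.

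Other places count differently:
- The Lay Summary (section 1) says "this study would require the evaluation of ~ 18380 bed movements and approximately 30 months to complete".
- Section 6 says "Total Number of Subjects to be Enrolled Across All Listed Sites Above (Auto Populated) 18680".
- Section 18 (HIPAA) speaks of more than 18,000 individual patients.

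The target of the test also varies. Section 11 describes equivalence, while section 19 describes non-inferiority or superiority. In section 3 the Objectives name escalation alone as the primary endpoint, but the endpoint list names a composite with RRT-initiated therapy and gives no rate for it.

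**The concern.** The paragraph contains two different targets: a 5% margin, and an expected reduction built from the 50% and 20% assumptions. One power figure is attached to both. A calculation for two proportions already uses the 10% rate and returns observations per arm. Dividing its result by 10% again would be a unit error, but the plan does not show whether that is what happened.

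What is at stake is how the result is read. If a superiority comparison came out null, a reader would set it against a claimed 95% power and take it as good evidence of no effect. At the plan's own minimum effect, a real reduction would be missed about 36% of the time two-sided or 25% one-sided. If instead the target was the 5-point margin and 934 was a per-arm count, about 93 days of accrual would have met it (934 / 10 per day), against the 934 days planned. Section 18 also rests its case that consent is impracticable on a count of individual patients, although 18,680 was derived as bed movements.

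**Working it through.** **Inputs.** Control rate 0.10, share identified at least 0.50, share of those prevented about 0.20, margin 5%, type 1 error 5%, power 95%, and 9,340 bed movements per arm (all section 19). Silent-pilot sensitivity 0.76 (section 3, Background). Sidedness is not stated, so both are shown. Bed movements are treated as independent.

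**1. Trying to reproduce 934.**

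*Reading A: a 5-point margin, 10% in both arms.* n per arm = 2 x 0.1 x 0.9 x (z1 + z2)^2 / margin^2.
- Rounded z: 0.18 x (1.96 + 1.64)^2 / 0.0025 = 933.1.
- Unrounded z: 935.6.

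This matches 934 as bed movements per arm. It needs non-inferiority at one-sided 2.5%, or equivalence by two one-sided 5% tests. One-sided 5% non-inferiority gives 780. A margin of 5% relative (0.5 point) gives 93,562. Superiority tests of 10% v 5% give 719 two-sided or 598 one-sided; 10% v 15% one-sided gives 945, also per arm.

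*Reading B: one-sample, one-sided 5% test of 9% against a fixed 10%.* n = [(1.645 x sqrt(0.09) + 1.645 x sqrt(0.0819)) / 0.01]^2 = about 9,297. An exact binomial test at n = 9,340 has power 0.9506. On this reading 9,340 is the calculated size, and 934 is the number of escalations expected at 10%.

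*Event-count formulas* for a 10% relative reduction at 95% power give 4,683 (two-sided) or 3,900 (one-sided) total events, not 934.

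**2. Power for a 5-point margin at 9,340 per arm.** SE = sqrt(0.18 / 9340) = 0.00439; margin / SE = 0.05 / 0.00439 = 11.4. Power is about 100%.

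**3. Power for the paragraph's own effect.** The reduction is 0.10 x share identified x 0.20. At 50% identified this is 0.01, so 10% v 9%.

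Power = Phi[(difference - z x SE0) / SE1], where SE0 uses the pooled rate and SE1 the separate rates. For 10% v 9%:
- SE0 = sqrt(2 x 0.095 x 0.905 / 9340) = 0.00429
- SE1 = sqrt((0.09 + 0.0819) / 9340) = 0.00429
- Two-sided: Phi[(0.01 - 1.96 x 0.00429) / 0.00429] = 0.645
- One-sided: Phi[(0.01 - 1.645 x 0.00429) / 0.00429] = 0.754

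A simulation of 400,000 trials gave 0.645 and 0.753.

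| Share identified | Rates compared | Two-sided 5% | One-sided 5% |
|---|---|---|---|
| 50% | 10% v 9.0% | 64% | 75% |
| 60% | 10% v 8.8% | 80% | 88% |
| 70% | 10% v 8.6% | 91% | 95% |
| 76% (pilot) | 10% v 8.48% | 94.8% | 97.4% |
| 80% | 10% v 8.4% | 97% | 98% |
| 100% | 10% v 8.0% | 99.8% | 99.9% |

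Power reaches 95% at about 76% identified two-sided or 70% one-sided, which are differences of about 1.5 and 1.4 points. For 10% v 9%, 95% power needs about 22,341 per arm two-sided or 18,606 one-sided.

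**4. Totals.** 2 x 9,340 = 18,680. The Lay Summary's 18,380 is 300 lower.

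**The case against.** The strongest objection is that no unit error need have occurred. Reading B uses the 50% and 20% assumptions, which Reading A leaves idle. It agrees with section 7's description of 934 as escalations expected among 9,340 bed movements. The Statistical Analysis text also lists binomial proportion tests first among its methods. Against it, Reading B ignores the stated margin, and exact binomial power is saw-toothed, so a match at 9,340 is not proof. A reader might infer from Reading A that 934 is certainly a per-arm count and that the study is ten times too large. The documents do not support that: they give no formula, and both readings fit. This part of the objection stands. It does not rescue the 95%, because Reading B treats the 10% as known without error, whereas the plan compares two concurrent groups of equal size.

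The second objection is that 10% v 9% is a floor. The plan says at least 50%, and its silent pilot reports a sensitivity of 0.76, at which two-arm power is essentially the stated 95%. This also stands. A reader might infer that the study is simply underpowered at 64%; that is true only at the minimum. But the paragraph states its power without tying it to 76% identified, and the figure it does give is 50%.

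Third, having more data than a 5-point margin needs does not invalidate a conclusion on that margin, and the final SAP analyses a different unit. Both are correct. They limit the harm to how the power statement is used, mainly in reading a null superiority result.

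**Conclusion.** The concern holds for the power statement. At 9,340 bed movements per arm, power is about 100% for a 5-point margin, and 64% two-sided or 75% one-sided for the smallest effect that the paragraph plans on. The 95% is approached only if about 76% (two-sided) or 70% (one-sided) of escalations are identified. Under neither reading of 934 does 95% hold for the two-arm comparison at 10% v 9%.

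The origin and unit of 934 remain open. The tenfold inflation is conditional on Reading A. The conflicts in totals and units are plain on the face of the text.

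These figures assume independent bed movements, a 10% control rate, 20% of identified escalations prevented, a margin in percentage points, and escalation alone as the endpoint. No power can be given for the composite, because its rate is not stated. None of the figures applies to the final SAP's analysis, which uses first hospitalisations with inverse probability weighting.

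**What to change.** (a) In section 19, replace the single power figure with two-arm power at 9,340 per arm:
- About 100% for the 5-point margin.
- 64% two-sided or 75% one-sided at 10% v 9%.
- 94.8% or 97.4% if 76% are identified.
- A detectable difference at 95% power of about 1.5 points two-sided or 1.4 one-sided.

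Beside each figure, state the hypothesis (sections 11 and 19 differ), the sidedness, the endpoint (the two statements in section 3 differ, and the composite needs a rate) and the independence assumption.

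(b) State the formula, test and unit that produced 934, and correct its label in sections 7 and 19 accordingly. The label should not be changed to bed movements per arm unless the authors confirm that this was the calculation.

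(c) Describe 18,680 as bed movements throughout, including sections 6, 7 and 18, and make the Lay Summary's 18,380 agree with 2 x 9,340.

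(d) Note in the final SAP that these power figures do not carry over to the weighted first-hospitalisation analysis, which has no stated size or power.

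The cost is wording only, and a less favourable stated power at the minimum effect. No bed movements and no study time are added.

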By only allowing only members of the investigational team to access PHI we protect subjects' privacy. All study personnel has completed HIPAA training, which ensures the utmost care is used to handle PHI.

Economic Impact on Subjects

There is no economic burden on the patient.

11. Procedures - Narrative

Description of the Study Design

Patients admitted to 10W and 10E meeting the inclusion and exclusion criteria will undergo a modified RRT evaluation protocol as detailed in Appendix 4: Process Flow. In brief, the patient will be evaluated based on our retrospectively validated machine learning algorithm (MEWS++) designed to improve identification of patients who may need care escalation. Patients on 9W and 9E will be followed but no alerts, interventions or changes from standard of care will be pursued. The study is designed to evaluate the equivalence in the proportion of escalations between the standard of care RRT protocol and our proposed ReSCUE-ME protocol. Patients admitted to 9W and 9E will not undergo any additional monitoring and thus will serve as controls.

Further details of the alerting system are listed below.

- a. Notifications can be suppressed or re-enabled on a per-patient basis. This is a core feature as it is needed to fulfill the opt-out process that we documented in our application's appendices.
- b. Currently there are several automated alerts sent to Vocera. These include ventilator and telemetry alarms, e.g. an alarm if the ECG monitor detects asystole. There is also a simple rules-based Epic BPA for hyperkalemia that sends an alert to the Vocera if a patient's potassium level is high. There is an administrative policy on alarm management that covers these existing alerts - Clinical Alarm Management GPP-242 – link to policy below: <http://policies.mountsinai.org/web/general-policies-and-procedures/policies/-/policy-management/viewPolicy/565852/>.

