#The basics of generating a MEWS++ score, the sources of the data and where the results will be made available to the floor patient care providers is described under "Procedures > Narrative" section of this IRB. Briefly, a random forest model has been trained to generate a prediction score based on 36 clinical variables. This score represents the likelihood of clinical deterioration. For all interim reports, final study outcome report, and publication analysis our research team plans to use an array of parametric and non-parametric statistical approaches to evaluate the significances of the primary and secondary endpoints. These would include, but not limited to binomial proportion tests, students t-tests, Mann-Whitney U test, Fisher's exact test, and ANOVA. Additionally, we plan to examine any potential significant difference in the demographics of the patients admitted to 10W and 10E when compared to 9W and 9E, significant differences will be incorporated into a multi-varient model such as a linear/logistic regression model to further elucidate factors that may have confounded the # of RRT evaluation and escalation events.

20. Data - Safety Monitoring

More Than the Minimum Data Safety Monitoring Will Be Done No

The following minimum requirements apply to all projects, including retrospective reviews of medical records, use of tissue samples, and many minimal risk studies, such as observational and survey research. Because these minimum requirements apply to all studies, a specific written DSMP will not usually be required for projects that do not pose greater than minimal risk to subjects. The MSSM PPHS may alter the required level of monitoring if appropriate.

For all projects, the principal investigator must have a plan to assure that data integrity will be maintained during its collection, storage and analysis. All research projects must adhere to MSSM recommendations on the storage of research data. Loss of data containing identifiable information is reportable to the IRB within 5 business days.

Any problems concerning the consent process and any subject complaints should be monitored by the investigator. Reports of such problems must be made at least annually. The discretion of the protocol director will guide the need to report these problems immediately or more frequently.

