Other - Other IRB Correspondance	Appendix 4b - Notification Process RRT.pdf	1	New	Appendix 4b - Notification Process RRT.pdf	03/05/2019
Other - Other IRB Correspondance	Appendix 5 - HRP416 Waiver of Consent Documentation	1	New	Appendix 5 - HRP416 Waiver of Consent Documentation.pdf	04/25/2019
Other - Participant Educational Materials	Appendix 1a - Waiver-Consent Information Sheet- CASES.docx	1	New	Appendix 1a - Waiver-Consent Information Sheet- CASES.docx	06/11/2019
	Appendix 1b - Waiver-Consent Information Sheet- CONTROLS.docx	1	New	Appendix 1b - Waiver-Consent Information Sheet- CONTROLS.docx	06/11/2019
Instruments	REDCap RRT Survey Placeholder.docx	1	New	REDCap RRT Survey Placeholder.docx	06/11/2019

Final Protocol

The final protocol was the same as the original protocol. No changes were made to the protocol during the study period.

Original Statistical Analysis Plan As submitted to the IRB Mar-June 2019

For all interim reports, final study outcome report, and publication analysis our research team plans to use an array of parametric and non-parametric statistical approaches to evaluate the significances of the primary and secondary endpoints. These would include, but not limited to binomial proportion tests, students t-tests, Mann-Whitney U test, Fisher's exact test, and ANOVA. Additionally, we plan to examine any potential significant difference in the demographics of the patients admitted to 10W and 10E when compared to 9W and 9E, significant differences will be incorporated into a multi-variant model such as a linear/logistic regression model to further elucidate factors that may have confounded the # of RRT evaluation and escalation events.

Final Statistical Analysis Plan

December 2021

Data from the first hospitalization for each patient during the study period were included in the study. The analyses focused on patient level, unit level, and alert level, individually. All variables were summarized using the appropriate descriptive statistics. Continuous variables were presented as mean (standard deviation) or median [interquartile range], as appropriate. Two-sample t test was used to examine differences in means and Kruskal-Wallis test was used to assess differences in median between study arms. Categorical variables were presented as count (percentage). Chi-square test was used for categorical variables associated different study arms.

Patient Level Analysis

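### Six-monthly significance evaluations have no error control, and the plan does not say whether a significant look could count as the trial's finding

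*Combined protocol and SAP*

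**What the plan says.** Protocol section 19 (Power Analysis, Sample size calculation) says that the sample size needed to "achieve a type 1 error of 5% and power of 95% is 934". The same paragraph then says that interim evaluations every six months "will be conducted and if at any point the model meets statistical significance or major flaws identified, a subsequent report will be submitted". Section 9 expects enrolment to take 30 months; section 7 puts it at about 934 days.

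The Statistical Analysis text in section 19, repeated in the Original Statistical Analysis Plan, reads "For all interim reports, final study outcome report, and publication analysis our research team plans to use an array" of tests, with the stated purpose "to evaluate the significances of the primary and secondary endpoints". The list of tests is open-ended and is the same for interim and final reports.

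The hypothesis is not settled. Section 11 says "The study is designed to evaluate the equivalence in the proportion of escalations", while section 19 says "We are specifying a non-inferiority or superiority margin of 5" per cent. Neither states sidedness.

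Under the Final Protocol heading the document says "No changes were made to the protocol during the study period", so the interim rule stood throughout. The final SAP of December 2021 mentions neither the interim evaluations nor any adjustment for them.

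**The concern.** A 5% type I error holds for one test at one time. Testing accumulating data at 5% on several occasions, and accepting significance whenever it appears, gives chance more than one opportunity. The usual safeguards are a group-sequential boundary, an alpha-spending function, or a plain statement that interim results carry no efficacy inference. The plan has none of these, and its trigger is significance at any look.

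At stake is what the stated 5% means. If a significant interim comparison of 10E/10W with 9E/9W could be put forward as the result, the error rate is well above 5%. If it could not, the final test keeps its level. The plan leaves the reader unable to tell, and has no rule for the case where an interim look is significant and the final test is not.

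**Working it through.** **1. The plan's own figure.** With a 10% rate in both groups and a margin of 5 percentage points:

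n per group = 2p(1−p)(z₁ + z₂)² / δ² = 2 × 0.10 × 0.90 × (1.960 + 1.645)² / 0.05² = 935.7.

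With z-values rounded to 1.96 and 1.64 it is 0.18 × 3.60² / 0.0025 = 933.1, which rounds up to 934. The formula fits non-inferiority at one-sided 2.5% with 95% power. It equally fits equivalence by two one-sided 5% tests with the 5% type II error split in two. Neither version includes an allowance for interim looks.

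**2. Number of looks.** Over 30 months, six-monthly evaluations fall at 6, 12, 18 and 24 months: four interim looks, plus the final analysis, making five.

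**3. Chance that any look is significant.** Assume equally spaced looks, independent observations and one test per look. Under the null, Z_k = S_k/√k, where S_k is the sum of k independent standard normal increments. The quantity is P(Z crosses the fixed critical value at one or more of K looks), found by recursive numerical integration:

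| Looks K | two-sided 5% (1.960) | one-sided 5% (1.645) | one-sided 2.5% (1.960) |
|---|---|---|---|
| 1 | 5.0% | 5.0% | 2.5% |
| 2 | 8.3% | 8.0% | 4.2% |
| 3 | 10.7% | 10.1% | 5.4% |
| 4 | 12.6% | 11.7% | 6.3% |
| 5 | 14.2% | 13.0% | 7.1% |

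A simulation of 2 million replicates at K = 5 gives 14.2%, 13.0% and 7.1%. With looks at 6, 12, 18 and 24 months and the final at day 934, the values are 14.3%, 13.1% and 7.1%, so exact spacing hardly matters. The one-sided columns also apply to non-inferiority with the true difference at the margin.

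**4. Equivalence.** Here the null is a true difference at the margin, and both one-sided tests must reject. With 934 per arm and five looks, the first look has 934/5 ≈ 187 per arm. At 15% v 10%, SE = √[(0.1275 + 0.09)/187] = 0.034, so the 90% interval half-width is about 1.645 × 0.034 = 0.056. This exceeds 0.05, so equivalence can hardly be declared that early and the inflation is smaller. Simulations give 10.5–12.3% over five looks; a binomial version with estimated variance gives 10.9–13.2%. Four looks go down to 9.2%. At 9,340 per arm the second test no longer binds and the five-look value is 13.0%. The range is roughly 9–13%, depending on sample size and test statistic.

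**5. Conflict between looks and final test.** Under a two-sided superiority test with five looks, the chance under no effect that some interim look is significant but the final test is not is 14.2% − 5.0% = 9.2%.

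**The case against.** The strongest reply is that the only stated consequence of a significant look is a report, in an application to an ethics board. Nothing says that the trial stops or that a claim is made. The analysis section names interim reports, the final outcome report and the publication analysis separately, which suggests that interim reports are not the finding. Elsewhere in the protocol the word model usually means the MEWS++ prediction model, so the trigger may concern predictive accuracy. On that reading the figures above do not apply to the between-arm comparison. Nor do the documents show that any look was run.

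Most of this stands, and it makes the inflation conditional. It does not remove the gap. The analysis section puts tests of the primary endpoint into every interim report, and no text says that those tests carry no inference.

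A reader might infer that this trial's actual error rate was 12–14%, or that it ran under an early-success rule. The documents do not support either. A reader might also take 12.6% as the false-report rate of the rule as written. But no two-sided test is written, and under an equivalence framing a significant look when the arms are truly equal is a correct result. The 12.6% and 9.2% are false-signal rates only for a two-sided superiority test.

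**Conclusion.** The gap is real and should be fixed, but its harm is conditional. If a significant between-arm look can count as the finding, the stated 5% becomes 12.6–14.2% (two-sided) or 11.7–13.0% (one-sided), about 2.3 to 2.8 times the nominal level. For non-inferiority at one-sided 2.5%, 2.5% becomes 6.3–7.1%, a similar ratio. Equivalence by two one-sided 5% tests gives roughly 9–13%. If only the final test counts, 5% holds.

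These figures rest on four to five equally spaced looks, independent observations and a single test per look. Choosing among several endpoints or tests at a look could raise them. The arithmetic is secure. Whether it applies depends on a statement that the plan does not make.

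**What to change.** **Protocol (needed before any look).** State that the six-monthly evaluations cover safety, alert burden and major flaws only and carry no efficacy claim. Section 10 already plans alert-burden trending and a review committee. Test the primary endpoint once, at the end, with one named test. This costs a few sentences and no power.

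If early efficacy claims are wanted, fix the hypothesis and sidedness first, then set matching group-sequential boundaries before any look. For example, O'Brien-Fleming with five equal looks at two-sided 5% uses |z| = 2.040 × √(5/k): 4.56, 3.23, 2.63, 2.28, 2.04. The maximum sample size rises by a factor of about 1.025 at 95% power.

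**Final SAP.** It reports event counts, so it was written after data were seen, and boundaries cannot be added now. Disclose which between-arm interim comparisons were run, on what data, and what each triggered. Base the primary conclusion on the single final analysis. If no look could have led to a claim, say so and keep 5%. If some could, report an adjusted final level, labelled retrospective. For equal spacing, a constant two-sided level is 0.029, 0.022, 0.018 or 0.016 for one, two, three or four such interim looks. The cost is one paragraph from existing records, with no new data.
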